2.8 Participant privacy and confidentiality

Individual subject medical information obtained as a result of this study is considered confidential and disclosure to third parties is prohibited. Subject confidentiality will be further ensured using unique subject identification code numbers to correspond to treatment data in any computer files.

The investigators affirm and uphold the principle of the participant's right to privacy and that they shall comply with applicable privacy laws. Especially anonymity of the participants shall be guaranteed when presenting the data at scientific meetings or publishing them in scientific journals.

For study related monitoring, audits, EC review and CA inspections, the investigator will provide direct access to source data and source documents including parts of patients' medical record relevant to the study (e.g. medical history) to authorised representatives of the Sponsor-Investigator, the CA, or a CEC.

2.9 Early termination of the study

Based on general expertise regarding the significance of the accumulating data, or other important reasons such as accumulating external evidence, quality concerns etc. the Sponsor-Investigator may terminate the study at any time. Termination will be in accordance with relevant regulatory, scientific, and ethical principles.

Premature study end or interruption of the study will be reported to the CEC to chapter 2.3.

2.10 Protocol amendments

Substantial amendments are only implemented after approval of the CEC.

Under emergency circumstances, deviations from the protocol to protect the rights, safety, and well-being of human subjects may proceed without prior approval of the sponsor and the CEC. Such deviations shall be documented and reported to the Sponsor-Investigator and the CEC as soon as possible.

All non-substantial amendments are communicated to the CEC within the Annual Safety Report (ASR).

3. BACKGROUND AND RATIONALE

3.1 Background and Rationale

Mental disorders are highly prevalent, undertreated, and associated with substantial disability and reduced quality of life (Demyttenaere et al., 2004). The 12 months prevalence of any mental disorder is 12% in Europe, whereby anxiety disorders and mood disorders are the most prevalent (Demyttenaere et al., 2004). One third of patients with mental disorders comorbidly suffer from insomnia disorder according to the Diagnostic and Statistical Manual of Mental Disorders (DSM-5) criteria (American Psychiatric Association, 2013, S. 5), i.e. persistent sleep disturbances and associated daytime impairments for at least three months (Seow et al., 2018). The prevalence of acute insomnia symptoms (< 3 months) is up to 68% in patients with mental disorders (Seow et al., 2018). Having comorbid acute or chronic insomnia is associated with significantly higher impairment compared to having a mental disorder without insomnia (Seow et al., 2018). As opposed to early lines of research aiming at the identification of disorder-specific patterns of sleep disturbance (e.g., early morning awakening as a marker of depression), recent work demonstrates that disruptions of sleep continuity (insomnia) represent a highly prevalent and trans-diagnostic problem in a wide range of mental disorders including anxiety disorders, affective disorders, schizophrenia, substance use disorders, eating disorders, borderline personality disorder and autism spectrum disorders (Baglioni et al., 2016).

Following current European and American practice guidelines for adult patients, cognitive behavioral therapy for insomnia (CBT-I) is the first line treatment (Qaseem et al., 2016; Riemann et al., 2017).

CBT-I is a treatment package including psychoeducation, restriction of time in bed, relaxation, and cognitive restructuring. Implementation of bedtime restriction is the best predictor for therapeutic success of CBT-I (Harvey, Inglis, & Espie, 2002), and bedtime restriction is also efficacious as a stand-alone treatment for insomnia (Miller et al., 2014). The major mechanism of action of bedtime restriction is an increase of homeostatic sleep pressure, thereby shortening sleep-onset latency and increasing sleep depth.

Various adaptations of CBT-I for different target groups and settings have been developed. One of them is Brief Behavioral Treatment for Insomnia (BBT-I), consisting of four sessions centering of bedtime restriction (Troxel, Germain, & Buysse, 2012). This demonstrates that brief versions of CBT-I can be similarly effective as the complete program.

In addition to shortening the program as in BBT-I, another promising approach for improving the implementation and dissemination of CBT-I is internet-assisted treatment using online programs or apps. This approach seems well feasible and effective in patients with insomnia without comorbidity (Seyffert et al., 2016). CBT-I and BBT-I have primarily been conceptualized and thoroughly evaluated for patients with primary insomnia, somatic comorbidity or minor psychiatric comorbidity (Trauer, Qian, Doyle, Rajaratnam, & Cunnington, 2015). A large number of trials has shown that in these patient groups, CBT-I and BBT-I improve insomnia with large effect sizes and can also improve comorbid mental symptoms such as mild depression with small to medium effect sizes (Ballesio et al., 2018). Both CBT-I and BBT-I, however, are insufficiently researched in patients with severe psychiatric disorders and symptoms including psychosis, severe addiction, borderline personality disorder and suicidality. These patients are rarely included because most trials are conducted in outpatient settings. Only a minority of studies have been conducted in psychiatric wards (Sheaves et al., 2016), and insomnia in this patient group is still frequently treated pharmacologically. According to current guidelines, however, CBT-I is also the first-line treatment for patients with insomnia and comorbid severe mental disorders (Riemann et al., 2017). Pharmacological treatment should only be considered if CBT-I is not available or not effective (Qaseem et al., 2016; Riemann et al., 2017). The reason is that the most thoroughly evaluated medication for insomnia, benzodiazepines and benzodiazepine receptor agonists, are not suitable for long-term treatment due to tolerance, dependency, and adverse effects such as cognitive impairment (Wilt et al., 2016). Together, the evidence for efficacy as a prerequisite for dissemination and implementation of CBT-I in patients with severe mental disorders, including those in an acute crisis, is insufficient.

The overarching objective of the proposed project is to target sleep to improve mental health. The specific aim is to investigate the efficacy of SleepExpert, a pragmatic behavioral treatment program for insomnia, in patients with severe mental disorders on psychiatric wards.

3.2 Investigational Product (treatment, device) and Indication

SleepExpert 1.0 is the first version of an online Program to treat Insomnia. The internet-based self-help platform used for the implementation of CBT-I in this study has been developed by the University of Bern ([name]. [name]), has been used successfully in previous trials (Krieger et al., 2019) and has received a CE mark in 2018.

The device is intended for patients with mental disorders and insomnia who are treated for mental disorders in a hospital or an outpatient unit.

A CE Declaration of Conformity will be submitted with this ethics application.

No parts of the device are in contact with body tissues or fluids, it is an online application. No specific training is needed to operate the application.

3.3 Preclinical Evidence

Not applicable, device does not need Swissmedic notification.

3.4 Clinical Evidence to Date

There is no available clinical research data to date on exactly this product (SleepExpert). However, the therapeutic content that is used in this study is based on Cognitive Behavioral Therapy for insomnia (CBT-I). This intervention has been found to be highly effective and without lasting adverse effects in many studies and is recommended for the treatment of insomnia in current clinical guidelines (Qaseem et al., 2016; Riemann et al., 2017). A meta-analysis of randomized controlled trials has shown that CBT-I is also effective and without adverse effects when delivered online (Seyffert et al., 2016).

3.5 Dose Rationale / Medical Device: Rationale for the intended purpose in study (pre-market MD)

In this study, SleepExpert will be applied in three steps, namely i) a face-to-face group session held by a psychologist or physician, ii) self-management with coaching by nurses, and iii) self-management without systematic support. This form of administration has been developed to adapt CBT-I, the gold standard treatment for insomnia, to the needs of patients with severe mental disorders and insomnia. Patients with severe mental disorders, especially those hospitalized on psychiatric wards in an acute crisis, often suffer from cognitive impairments and motivational problems that make it impossible to implement CBT-I as usual. The gradual adaptation of support from face-to-face therapy to self-management is supposed to make CBT-I accessible for this specific patient group.

3.6 Explanation for choice of comparator (or placebo)

SleepExpert, an app-assisted treatment program with a face-to-face component, will be embedded into routine clinical care (treatment-as-usual, TAU). The comparison group in this trial will receive inpatient psychiatric treatment-as-usual (TAU) plus sleep monitoring. TAU comprises standard clinical care, including intensive daily contacts with health care providers on the wards, medical treatment, pharmacotherapy, psychotherapy in individual and group setting, nurse support, additional therapies such as music or ergotherapy and social support, informed by current guidelines for the respective disorder and adapted to individual needs. Of note, no change to any aspects of TAU will be made. Sleep monitoring will consist of daily sleep diary entries with the help of a smartphone app. In contrast to the SleepExpert version, the sleep monitoring version will not give any feedback or advice concerning sleep behavior. Patients in the control group will receive TAU plus sleep monitoring, whereas patients in the experimental group will receive TAU plus SleepExpert. We chose TAU, and not an active placebo control, as a comparator for the following reasons: Placebo control groups are mostly used to control for unspecific effects of attention by health professionals or contact with other patients. In our trial, patients in the TAU group will also get an extensive level of daily attention by health professionals and will also have the possibility to get to know other patients with similar problems. SleepExpert will be associated with a minimal amount of added therapist attention and contact time. Thus, an active control group is not necessary to control for these context aspects. Moreover, participants in an active control group would likely notice that they receive a "dummy treatment" that is unlikely to improve their sleep. This would reduce motivation to participate, may increase the dropout rate and reduce validity. Due to the inpatient and selected setting, TAU, in this study, can be well controlled and described and will be comparable across groups.

3.7 Risks / Benefits

The study will potentially be associated with direct advantages for the participating patients and indirect / potential advantages for the treatment of sleep disorders in patients with mental disorders in the case of positive results. No health related or other ethical problems are expected for the participants. Thus, the benefits of the study are supposed to outweigh the risks.

3.8 Justification of choice of study population

Patients with mental disorders and insomnia have been chosen because insomnia is highly prevalent in patients with mental disorders and the goal of this study is to improve treatment options for insomnia in this group. No vulnerable participants will be included into the study. Minors and patients incapable of judgement or under tutelage for health issues will be excluded from participation in the study. During the screening procedures, it will be made sure that patients understand the purpose and content of the study, potential risks and benefits, and that patients are able to comply with the study procedures (participation in group session, handling of web application). Patients who do not fulfil these criteria will be excluded from participation.

4. STUDY OBJECTIVES

4.1 Overall Objective

The main hypothesis is to investigate whether SleepExpert improves insomnia and general mental health in patients with severe mental disorders.

4.2 Primary Objective

The primary objective is to assess whether there is a significantly greater reduction in self-assessed insomnia severity (as measured by the Insomnia Severity Index, ISI) across six months (interaction effect Group and Timepoint) in patients in the Tau plus SleepExpert group, compared to patients in the TAU plus sleep monitoring group.

4.3 Secondary Objectives

The secondary objective is to assess whether there is a significantly greater improvement in general mental health (Brief Symptom Inventory) across six months (interaction effect Group and Timepoint) in patients in the TAU plus SleepExpert group, compared to patients in the TAU plus sleep monitoring group.

4.4 Exploratory objectives

Exploratory objectives include the effect of TAU plus SleepExpert versus TAU plus SleepMonitoring on the following parameters:

- Severity of depressive symptoms (Beck Depression Inventory, BDI)
- mood, tiredness, concentration, and subjective sleep quality (self-constructed visual analogue scales)
- Daytime sleepiness (Epworth Sleepiness Scale)
- Medication
- Hospitalization

4.5 Safety Objectives

The study aims to assess short- and long-term safety of SleepExpert and its tolerability in terms of incidence of sleep- and mental-health related side effects and use of sleep medication.

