1. STUDY ADMINISTRATIVE STRUCTURE

1.1 Study Plan

Table 1. Patient schedule

	screening	T0	T1 (week1)	T2 (week2)	T3 (week12)	T4 (week 26)	debriefing***
Time point (days)	at or after admission to ward until T 0	0	7±2	14±2	84±7	182±7	
Eligibility screen	x						
Informed consent	x (signature 24 hours or more after first information)						
Medical History	x						
Insomnia Severity Index	x	x	x	x	x	x	
Brief Symptom Inventory		x		x		x	
Beck Depression Inventory		x		x		x	
Visual analogue scales*		x	x	x	x	x	
Daily sleep Diary**			x	x	x	x	
Medication status	x	x	x	x	x	x	
TAU plus SleepExpert							
TAU plus sleep monitoring***							
Adverse Events		x	x	x	x	x	

* self-constructed visual analogue scales will be used to measure subjective sleep quality, mood, concentration, and tiredness

** the sleep diary will be used continuously throughout the study period (baseline until T4)

*** debriefing: All patients, i.e. the TAU plus sleep monitoring and TAU plus SleepExpert group will have an individual appointment with a sleep expert (physician or psychologist) after completion of the study, i.e. after 6 months, in which the gathered information (sleep diaries and actigraphy data) will be discussed and individualized further diagnostics and treatments, if needed, will be initiated.

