2.2 Categorisation of study

The psychotherapeutic protocol used in this study (Cognitive Behavioral Therapy for Insomnia) is non-invasive. Comparable therapeutic protocols have been thoroughly investigated in patients with insomnia without adverse events. Sleep restriction as used in this therapy may be associated with temporary daytime sleepiness. No long-lasting or serious adverse effects of these psychotherapies are known. In addition, multiple previous studies have shown that Cognitive Behavioral Therapy for insomnia is also feasible as an online application. The new aspect of this study is a change of the target group: instead of patients with insomnia only, the intervention will be applied in patients with insomnia and mental disorders (both disorder groups are category F in the ICD-10). We have no reason to assume that the psychotherapeutic protocol is associated with unexpected risks in this target group. The internet-based self-help program platform developed by [name], University of Bern, that will be used in this study has received a CE mark in 2018 that is valid for 5 years. All examinations and interventions in this study are in accordance with current safety standards and the risk associated with a participation in this study is regarded as minimal. Thus, this study belongs to category A.

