5.3 Exploratory Outcomes

Exploratory outcomes will be the severity of depressive symptoms (Beck Depression Inventory, BDI) (Beck et al., 1988), self-constructed visual analogue scales measuring mood, tiredness, concentration and subjective sleep quality, daytime sleepiness (Lapin et al., 2018), medication (self-reported) and hospitalization (self-reported number of inpatient stays within the follow-up period). Timepoints when the different exploratory outcomes will be administered can be found in table 1 (section 9.1).

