9.3.2 Timepoints T0 to T4

Time point T0 (day 0):

- Insomnia Severity Index
- Brief Symptom Inventory
- Beck Depression Inventory
- Visual analogue scales (subjective sleep quality, mood, concentration, and tiredness)
- Sleep diary will be handed out
- medication status
- adverse events

Time point T1 (day 7±2):

- Insomnia Severity Index
- Visual analogue scales (subjective sleep quality, mood, concentration, and tiredness)
- sleep diary will be checked
- medication status
- adverse events

Time point T2 (day 14±2):

- Insomnia Severity Index
- Brief Symptom Inventory
- Beck Depression Inventory
- Visual analogue scales (subjective sleep quality, mood, concentration, and tiredness)
- sleep diary will be checked
- medication status
- adverse events

Time point T3 (day 84±7):

- Insomnia Severity Index
- Visual analogue scales (subjective sleep quality, mood, concentration, and tiredness)

- sleep diary will be checked
- medication status
- adverse events

Time point T4 (day 182±7):

- Insomnia Severity Index
- Brief Symptom Inventory
- Beck Depression Inventory
- Visual analogue scales (subjective sleep quality, mood, concentration, and tiredness)
- sleep diary will be checked
- medication status
- adverse events

For details regarding the mentioned questionnaires, please see chapter 5.

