10.3.1 Foreseeable adverse events and anticipated adverse device effects

Potential adverse events are transitional worsening of the sleep disorder and / or the mental disorder, daytime tiredness and daytime sleepiness. No SAE that could be related to the investigational device or study procedures are expected during this clinical trial.

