11. STATISTICAL METHODS

11.1 Hypothesis

Hypothesis: SleepExpert improves insomnia and general mental health in patients with severe mental disorders.

Primary objective: To assess whether there is a significantly greater reduction in self-assessed insomnia severity (as measured by the Insomnia Severity Index, ISI) across six months (interaction Group x Time) in patients in the Tau plus SleepExpert group, compared to patients in the TAU plus sleep monitoring group.

Secondary objective: To assess whether there is a significantly greater improvement in general mental health (Brief Symptom Inventory) across six months (interaction Group x Time) in patients in the TAU plus SleepExpert group, compared to patients in the TAU plus sleep monitoring group.

Exploratory objectives: Additional objectives include the effect of TAU plus SleepExpert versus TAU plus SleepMonitoring on the following parameters:

- severity of depressive symptoms (Beck Depression Inventory, BDI)
- mood, tiredness, concentration, and subjective sleep quality (self-constructed visual analogue scales)
- daytime sleepiness (Epworth Sleepiness Scale)
- medication
- hospitalization

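### Daytime sleepiness is a named outcome and a foreseen harm, but no visit schedules the Epworth scale that is meant to measure it

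*Combined protocol and SAP*

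**What the plan says.** **Sleepiness as a foreseen harm.** Section 2.2 states: "Sleep restriction as used in this therapy may be associated with temporary daytime sleepiness". Section 10.3.1 begins its list with "Potential adverse events are transitional worsening of the sleep disorder" and goes on to worsening of the mental disorder, daytime tiredness and daytime sleepiness. Tiredness and sleepiness are separate entries. The safety objective in 4.5 is to assess tolerability through the "incidence of sleep- and mental-health related side effects and use of sleep medication".

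**Sleepiness as an outcome.** Section 4.4 lists "Daytime sleepiness (Epworth Sleepiness Scale") among the exploratory objectives, and 11.1 repeats "daytime sleepiness (Epworth Sleepiness Scale"). Sections 5.3 and 9.2.3 list daytime sleepiness as an exploratory outcome with a literature citation but do not name the scale.

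**Timing.** Section 5.3 says: "Timepoints when the different exploratory outcomes will be administered can be found in table 1 (section 9.1"). Section 9.1 in turn points to the table in section 1.1.

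**What the schedule holds.** Table 1 has rows for the ISI, the BSI, the BDI, visual analogue scales, the sleep diary, medication status and adverse events. Its footnote says that "self-constructed visual analogue scales will be used to measure subjective sleep quality, mood, concentration, and tiredness". Section 9.3.2 lists the same instruments visit by visit, including "Visual analogue scales (subjective sleep quality, mood, concentration, and tiredness"). Neither place has an Epworth or other sleepiness item.

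**Safety questioning.** Sections 5.4 and 9.2.4.1 describe one question to patients at T0 to T4, about negative life events. Section 10.3 requires all adverse events to be collected from consent to the last study procedure.

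**The concern.** An outcome with a named instrument and no scheduled administration cannot be analysed. Section 11.4 defers the statistical analysis plan to the start of recruitment. That plan can define variables and tables, but it cannot recover a questionnaire that was never given. The timing makes this worse: the sleepiness is expected to be temporary, so data from the first two weeks cannot be collected afterwards.

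The gap falls on a harm that the protocol itself attributes to the active ingredient of the treatment. Section 2.2 describes the target group as the new aspect of the study, and 11.2 makes a large confirmatory trial conditional on encouraging pilot results. If sleepiness is recorded only when it surfaces as an adverse event, a low count is hard to interpret. It could mean good tolerability, or it could mean that the question put to patients did not bring sleepiness out.

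**Working it through.** The main check compares sections and needs no formula.

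**Step 1. Foreseen harms (10.3.1) against scheduled patient measures at T0 to T4 (Table 1 and 9.3.2).**

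| Foreseen harm | Scheduled measure | Visits |
|---|---|---|
| Worsened sleep | ISI | 5 of 5 |
| Worsened mental symptoms | BSI | 3 of 5 (T0, T2, T4) |
| Daytime tiredness | Visual analogue scale | 5 of 5 |
| Daytime sleepiness | None dedicated (Epworth named, not scheduled) | 0 of 5 |

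Table 1 and the plain lists in 9.3.2 agree, so a table damaged in text extraction does not explain the absence.

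**Step 2. What is collected anyway.** An adverse-event item stands at all five visits. Medication status is recorded at screening and at all five visits. Section 11.4.4 compares adverse-event categories between groups.

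**Step 3. How much depends on sleepiness surfacing as an adverse event (illustration).** The documents give no sleepiness rates and no figure for how much sleepiness would come to light. Assume 30 patients per arm (half of 60) and that a share s of true sleepiness is recorded, with s = 1, 0.5 or 0.25.

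With zero reports among 30 SleepExpert patients, the one-sided 95% upper limit for the reported rate is 1 − 0.05^(1/30) = 0.095. The corresponding limit for the true rate is 0.095/s:
- s = 1: 9.5%
- s = 0.5: 0.095/0.5 = 19%
- s = 0.25: 0.095/0.25 = 38%

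Power of the chi-square test in 11.4.4 (exact enumeration, two-sided 0.05, 30 per arm, ignoring clustering and dropout), with both assumed true rates multiplied by s:

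| Assumed true rates | s = 1 | s = 0.5 | s = 0.25 |
|---|---|---|---|
| 50% vs 20% | 0.69 | 0.34 | 0.18 |
| 40% vs 20% | 0.39 | 0.19 | 0.11 |

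The comparison is weak even with full reporting unless the difference is large, and incomplete reporting weakens it further.

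**Step 4. What the Epworth scale would give.** The 95% half-width for a difference in means with 30 per arm is t(0.975, 58) × √(2/30) = 2.002 × 0.258 = 0.52 SD. This also ignores clustering by ward and dropout. Dropout would widen the interval, and clustering would probably do so too.

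**Step 5. Burden.** T0 to T2: 60 × 3 = 180 questionnaires. T0 to T4: 60 × 5 = 300.

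**The case against.** The strongest reply is that the safety plan works without the Epworth scale. Section 10.3 collects all adverse events, each visit has an adverse-event item, and 5.4 has events categorised by type, severity and relatedness. Sleepiness is on the list in 10.3.1, so staff know to look for it. As inpatients, both arms have daily contact with clinicians and nurses, and SleepExpert nurses discuss sleep behaviour with patients twice a week. Stays typically last one to eight weeks (8.1.1), so many patients would still be on the ward at T1 and T2. The ISI includes daytime impairment, and the visual analogue scales cover tiredness and concentration. The Epworth is labelled exploratory, and no safety section names it.

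Most of this stands, and it rules out two stronger readings. A reader might infer that the safety plan as a whole does not match objective 4.5. The documents do not support that: three of the four foreseen harms have scheduled measures, all adverse events are recorded, and medication status is collected throughout, so sleep-medication use can be extracted. A reader might also infer that no one would ask about sleepiness. The text does not say that the visit item is limited to the life-events question or to volunteered reports. It only describes no other question. Nor does 11.2 say that adverse-event counts will decide whether the confirmatory trial goes ahead.

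The reply leaves the schedule gap untouched. Calling the outcome exploratory does not make it measurable, and 10.3.1 itself separates sleepiness from tiredness. Deleting the scale from 4.4 and 11.1, and sleepiness from 5.3 and 9.2.3, would restore consistency. It would also leave the one foreseen harm without a dedicated measure.

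**Conclusion.** The point holds as a specific inconsistency between outcomes and schedule, with a consequence for safety reporting. The Epworth scale is given at 0 of 5 visits, so the stated sleepiness outcome cannot be analysed, and evidence on sleepiness would rest on general adverse-event recording. This conclusion comes from the text alone. The limits of 9.5% to 38% and the power figures show direction only, because the rates and reporting shares behind them are assumed. The correction is worth making before recruitment, because early data cannot be collected later. The primary ISI result is unaffected, and the point is no criticism of adverse-event collection as a whole.

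**What to change.** Add an Epworth row to Table 1 and an Epworth entry to 9.3.2 at T0, T1 and T2 at least, since the effect is expected early and to pass. T0 to T4 is preferable, because 4.5 covers long-term safety too. Name the scale in 5.3 and 9.2.3. Report mean and SD by arm and visit, and show the same table beside the adverse-event results. No new model or visit is needed.

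Optionally, add one direct question on daytime sleepiness to the existing adverse-event item, worded identically in both arms. The life-events question can stay.

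The cost is 180 short questionnaires (T0 to T2) or 300 (T0 to T4) and an amendment under 2.10. There are three drawbacks. Patients are not blinded (6.2.2), so those on SleepExpert may over-report sleepiness. A direct question would raise adverse-event counts in both arms. With about 30 per arm, only large differences will show, so the results should be read as description.
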